Potential study subjects will be identified from a pool of candidates for SCS therapy that are either affiliated with or referred to the clinical sites. Notice of availability of the study may be used for recruitment purposes, upon approval of the patient recruitment materials by the study IRB(s). An informed consent form (ICF) will be given to the potential subject for private evaluation. The Investigator or Study Clinical Staff will be available to respond to any questions the potential subject may have during evaluation of the ICF. Potential study subjects willing to participate in the study will visit the study site for providing written consent and for evaluation of eligibility based on inclusion and exclusion criteria. Subjects may also be consented via a combination of mail and telephone calls. The RC will document the telephone calls and follow-up by signing the consent once the subject returns the signed consent. The RC will then provide a photo copy to the subject. Once a consented subject is deemed qualified to participate in the study, baseline assessments and randomization will occur followed by scheduling of the trial stimulation phase with the assigned treatment group. Subjects who complete a successful SCS trial phase will be scheduled to receive a permanent implant of leads and the implanted neurostimulator (INS) and will undergo 12 months of stimulation delivery with assessments at 1, 3, 6, 9, and 12 months after the activation of the therapy.

All subjects who remain implanted at or after the 6 month visit, but are not getting sufficient pain relief and would like to try the other treatment arm's parameters will have the option to cross over to the other treatment group (this is an optional two-way crossover). X-ray may be required to determine lead locations. Crossover must be completed within 30 days of the 6 month visit.

Baseline assessments will include measures for pain intensity, use of medication, extent of disability, and quality of life.

Following completion of the baseline assessment, study subjects will be randomized in a 1:1 ratio to either the DTM-SCS programming group or the Conventional SCS programming group.

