B.7. Study Endpoints

B.7.1. Definition of Analysis Populations

- Modified Intent to Treat (mITT): All successfully randomized subjects who complete the Trial Phase.
- Intent-to-Treat (ITT): All successfully randomized subjects who met all the enrollment criteria.
- Per-Protocol (PP): All subjects who received a permanent device implant and contributed their data to the 3-month endpoint without any major protocol deviations or adverse events (that would render their data unevaluable).

The primary analysis of the primary and secondary endpoints will be performed on the mITT population. Supportive analyses will be performed for the Intent-to-Treat and Per-Protocol population.

For analyses incorporating crossover data (i.e. data gathered in the post 6-month periods), analyses will be based on the mITT population with treatment group defined by the treatment status at the corresponding time point to capture the impact of crossover. Additional sensitivity analyses censoring data post-crossover will be performed to examine the impact of crossover.

B.7.2. Effectiveness Assessment Definitions

- Primary Effectiveness Assessment: For subjects who have a successful Trial Phase and receive a permanent implant, the Primary Efficacy Assessment occurs at the follow up visit 3 months after Device Activation. For subjects who do not have a successful Trial Phase (based on subject's pain score) or subjects who do not want a permanent device implant due to insufficient pain relief (based on subject's discontinuation reason), the Primary Efficacy Assessment occurs at the end of the Trial Phase.

B.7.3. Primary Endpoint

Pain rating on the 10 cm Visual Analog Scale is considered the primary outcome measure. VAS is the most widely used outcome measure in assessing pain due to its documented reliability and validity, ease in administration, and minimal training requirements for the administrator.

- ***Individual Responder:*** A decrease in back pain VAS by at least 50% at 3 months after Permanent Device Activation as compared with Baseline. All subjects must be using the assigned programming parameters. If a subject is switched to a programming parameter that is not considered to be DTM-SCS nor Conventional SCS programming the subject will be counted as a non-responder for the following follow-up visit if one of the two following conditions exist:

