 - If a subject is switched to a programming parameter that is not considered to be DTM-SCS nor Conventional SCS programming for a period over two weeks
 - If a subject is switched to a programming parameter that is not considered to be DTM-SCS nor Conventional SCS programming for any length of time within the 2 weeks prior to a follow-up visit.

Overall Study Success: The percentage of Individual Responders in the test group is shown to be statistically non-inferior to the percentage in the control group.

B.7.4. Secondary Endpoints

The following secondary endpoints will be evaluated:

- Comparison of the percentage of Individual Responders between the test and control groups in a statistical test of superiority over time (i.e. based on repeated measures analysis). In addition, data will be summarized at the individual time points at 3 months, 6 months, 9 months, and 12 months. This will be performed based on all observed data with treatment defined as a time dependent covariate, and additionally based on censoring data post-crossover.

- Comparison of change from Baseline in back pain score (VAS) between test and control in statistical tests of non-inferiority and superiority. This is calculated as: Change from Baseline in Back Pain VAS = Follow-up Visit Pain VAS – Baseline Pain VAS. A negative result reflects a decrease in the Pain VAS, while a positive result reflects an increase in Pain VAS. All subjects must be using the assigned programming parameters. If a subject is switched to a programming parameter that is not considered to be DTM-SCS nor Conventional SCS programming, that subject's Baseline Back Pain VAS will be used instead of Follow-up Visit VAS after the programming change has occurred for the following follow-up visit if one of the two following conditions exist:
 - If a subject is switched to a programming parameter that is not considered to be DTM-SCS nor Conventional SCS programming for a period over two weeks
 - If a subject is switched to a programming parameter that is not considered to be DTM-SCS nor Conventional SCS programming for any length of time within the 2 weeks prior to a follow-up visit.

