Analysis of both secondary endpoints will be based on a repeated measures approach that accounts for within subject correlation. Treatment group status for the repeated measures models will be based on treatment status at the current time point (i.e. it will be based on treatment status incorporating potential crossover, not necessarily the original randomized assignment).

B.7.5. Additional Data Collection

These following data will be collected:

- Frequency of treatment emergent adverse events
- Comparison of opioid medication usage from baseline at 3, 6, 9 and 12 months after device activation between the two arms
- Comparison of mean change from Baseline in Leg Pain VAS, evaluated at 3, 6, 9 and 12 months after device activation for subjects with baseline leg pain VAS score ≥ 5 between test and control
- Comparison of Leg Pain Treatment Success, measured as at least a 50% reduction in Leg Pain VAS, evaluated at 3, 6, 9, and 12 months after device activation for subjects with baseline leg pain VAS score ≥ 5 between test and control
- Comparison of patient satisfaction between two arms
- Patient Global Impression of Change, evaluated at 3, 6, 9 and 12 months after device activation
- Comparison of Patient Global Impression of Change between two arms

- Comparison of ODI change from baseline at 3, 6, 9 and 12 months after device activation between the two arms
- Comparison of quality of life (QoL) change (from EuroQol EQ-5D-5L) from baseline at 3, 6, 9 and 12 months after device activation between the two arms
- Quality of paresthesia at 3, 6, 9 and 12 months, comparison between test and control
- Percentage of subjects that crossover
- Comparison of mean change from last visit prior to crossover to 12 months visit. This analysis censors data post-crossover.
- Activity level based on Intellis™ adaptive data log (when available)
- Analysis of additional evaluable data items will be based on treatment status at the current time point (i.e. it will be based on treatment status incorporating potential crossover, not necessarily the original randomized assignment).

B.8. Evaluation Criteria

B.8.1. Effectiveness

Results of the tests and standard questionnaires will be recorded in Case Report Forms at Baseline and during follow-up visits. Changes from Baseline will be calculated and compared between the two groups.

Effectiveness will be measured for each subject using the following tests:

- Pain

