 - Visual Analog Scale (VAS, 10 cm) at Baseline, End of Trial Phase, Months 1, 3, 6, 9 and 12
- Disability
 - Oswestry Disability Index Questionnaire
- Quality of Life
 - EuroQol EQ-5D-5L
- Impression of Change in Quality of Life
 - Patient Global Impression of Change
- Satisfaction with Therapy
 - Subject Satisfaction Questionnaire

Study personnel will be appropriately trained for administration of each test.

B.8.2. Definition of Success

The subject's self-reported pain intensity score based on the 10 cm Visual Analog Scale (VAS) is considered the outcome measure for the efficacy component of the primary endpoint. VAS is a widely used outcome measure in assessing pain. It is a reliable and valid

method, which is easy to administer, and requires minimal training for the test administrator. VAS scores will be collected for both back and leg pain.

Study success will be declared if the non-inferiority test for the primary effectiveness endpoint is statistically significant.

There are no additional pre-specified subject or study-level success criteria for secondary and tertiary endpoints.

B.8.3. Safety

Safety will be assessed by characterizing adverse events at all study visits with descriptive statistics.

B.8.3.1 Definitions

An adverse event (AE) is any untoward medical occurrence in a subject associated with the use of the therapy under the study whether or not related to Intellis™ SCS system or the study procedures. An AE is also any event related to any underlying medical condition, present at baseline, which increases in severity or frequency by a clinically meaningful amount during the study as determined by the Investigator.

For all adverse events, the Investigator will provide an assessment of the relationship to the study. If the adverse event is study-related, the following parameters will be assessed: its seriousness, severity, treatment/intervention provided, and resolution.

As the efficacy measures in this study are back and leg pain, back and leg pain do *not* need to be reported as an adverse event unless it meets the definition of a serious adverse event. Investigators may, however, report any other pain-related adverse events during the study.

Pre-existing conditions will not be reported as an adverse event unless there has been a substantial increase in the severity or frequency of the problem, which has not been attributed to its natural history.

A serious adverse event (SAE) is an adverse event that

- Leads to death

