Activity	Pre-Trial Phase			Trial Phase		Permanent Implant (up to 60 days after end of trial)	Permanent Implant Phase Follow-up					
	Enrollment	Baseline	Randomization	Start Trial Phase	End Trial Phase (up to 10 days after start of trial)		Device Activation (0-14 days after implant)	1-month visit (±15 days after activation)	3 months visit (±21 days after activation)	6 months visit (±31 days after activation)	9 months visit (±31 days after activation)	12 months visit (±45 days after activation)
Informed Consent	X											
Pain Intensity Evaluation (VAS)	X				X			X	X	X	X	X
Medication Use	X	X		X	X	X	X	X	X	X	X	X
Medical/Surgical History	X	X										
Eligibility Criteria Evaluation	X											
Disability Assessment (ODI)	X							X	X	X	X	X
Quality of Life Assessment (EQ-5D-5L)		X						X	X	X	X	X
Randomization			X									
AP/Lateral x-ray imaging				X	[X]	X	[X]	X	[X]	[X]	[X]	[X]
Paresthesia Questionnaire								X	X	X	X	X
Patient Global Impression of Change								X	X	X	X	X
Subject Satisfaction								X	X	X	X	X
Adverse Event Monitoring	X		X	X	X	X	X	X	X	X	X	X
Device Programming				X		X	[X]	[X]	[X]	[X]	[X]	[X]
Device Log								[X]	[X]	[X]	[X]	[X]
Cross over									[X]			
Study Completion					X ^a							X

^a For subjects that do not have a successful Trial Phase.

[X] Optional activity.

B.9.2. Statistical Analysis

Descriptive statistics will be used to summarize baseline and outcome data collected during the study. Continuous variables will be summarized using means, standard deviations, and ranges. Categorical variables will be summarized in frequency distributions. Repeated measures models will account for within subject correlation by use of a compound-symmetric covariance structure (based on logistic regression/generalized estimating equations for binary variables, and linear repeated measures models for continuous variables).

B.9.2.1 Primary Analyses

The *primary efficacy endpoint* will be evaluated with a Farrington-Manning binomial test for non-inferiority with a 10% margin at the one-sided 0.05 alpha level.

H_0 : The percentage of subjects (P) who achieve a 50% improvement in their back VAS pain score at 3 months in the Test group is inferior to that in the Control group.

$$P_{\text{Test}} \leq P_{\text{Control}} - 10\%$$

H_1 : The percentage of subjects (P) who achieve a 50% improvement in their back VAS pain score at 3 months in the Test group is not inferior to that in the Control group.

$$P_{\text{Test}} > P_{\text{Control}} - 10\%$$

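### B.9.2 fixes compound symmetry for every repeated-measures model while treatment can switch within subject; if correlation decays over time and a material share cross over, the linear-model intervals for VAS change are too narrow

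*Combined protocol and SAP*

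**What the plan says.** B.9.2 sets one rule for all repeated-measures analyses: within-subject correlation is handled "by use of a compound-symmetric covariance structure". It covers both model families: "based on logistic regression/generalized estimating equations for binary variables, and linear repeated measures models for continuous variables". It does not say whether standard errors are model-based or robust, and it names no second structure. B.9.2.4 leaves to a separate analysis plan only the details of imputation.

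B.7.4, and again B.9.2.2, state: "Treatment group status for the repeated measures models will be based on treatment status at the current time point". For the responder endpoint, B.7.4 plans an analysis "with treatment defined as a time dependent covariate, and additionally based on censoring data post-crossover". B.7.1 adds: "Additional sensitivity analyses censoring data post-crossover will be performed to examine the impact of crossover".

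On timing, B.6.1 says: "Crossover must be completed within 30 days of the 6 month visit". B.8.1 lists the pain assessments: "Visual Analog Scale (VAS, 10 cm) at Baseline, End of Trial Phase, Months 1, 3, 6, 9 and 12". Months 3 and 6 therefore precede any switch, and months 9 and 12 follow it.

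The two sections differ on status. B.7.4 speaks of superiority testing for responders, and of non-inferiority and superiority testing for VAS change, and says both endpoints use repeated measures. B.9.2.2 attaches neither a hypothesis nor an alpha to the repeated-measures comparisons. Its formal tests are at 3 months.

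**The concern.** Compound symmetry assumes one variance at all visits and the same correlation for visits 3 months apart as for visits 9 months apart. When treatment is fixed for each subject, the average treatment effect is a between-subject contrast, and its standard error tolerates a wrong correlation pattern. Once treatment switches after month 6, part of the effect is estimated from each switcher's later visits against the earlier ones. The model-based variance of that part depends directly on the assumed pattern. If nearby visits correlate more than distant ones, it is understated.

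GEE is usually reported with sandwich errors, which protect against this. A linear repeated-measures model by default is not, and the plan does not ask for it. At stake are the between-arm intervals for back pain VAS beyond 3 months. B.7.5 applies the same current-treatment rule to the additional data items, which include leg pain, ODI and EQ-5D-5L.

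**Working it through.** **The plan's own figure.** The documents give no error rate for these models. The nearest figure is the primary sample size in B.5.5.1 (70% v 50%, margin 10 points, one-sided 0.05, 50 per arm). The Farrington-Manning calculation gives 92.7% power, which agrees with the stated 90% or more. It does not use the repeated-measures model.

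**Inputs.** From the documents: 100 subjects, 1:1; visits 3, 6, 9 and 12; switching only after month 6; compound symmetry; current treatment as covariate. Assumed: the true correlation and the share crossing over.

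**Step 1: the mechanism by hand.** Take autoregressive correlation of 0.7 per 3 months and unit variance. The six pairwise correlations are 0.7 (three times), 0.49 (twice) and 0.343, with mean 3.423/6 = 0.5705. A compound-symmetric fit settles near this value (0.57 in the simulations).

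- Between-subject part, variance of the four-visit mean. True: (4 + 2 × 3.423)/16 = 0.678. Compound symmetry: (1 + 3 × 0.5705)/4 = 0.678. They are identical, so without crossover nothing is lost.
- Within-subject part, mean of months 9 and 12 minus mean of months 3 and 6. True: (1 + 0.7) − 2 × (0.7 + 2 × 0.49 + 0.343)/4 = 1.7 − 1.0115 = 0.6885. Compound symmetry: 1 − 0.5705 = 0.4295. Standard error ratio: √(0.4295/0.6885) = 0.79.

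The same arithmetic gives 0.83 at autoregression 0.5 and 0.76 at 0.9. The treatment estimate mixes both parts, so its ratio lies between these values and 1.

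**Step 2: simulation with no treatment effect.** 100 subjects, four visits, compound symmetry by REML, random crossover in equal shares of both arms, 10,000 replicates (Monte Carlo error √(0.05 × 0.95/10,000) = 0.2 points).

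| True correlation | Crossover | SE ratio | One-sided 5% | Two-sided 5% | One-sided, sandwich |
|---|---|---|---|---|---|
| AR 0.5 | 0% | 1.01 | 4.8% | 4.8% | 4.6% |
| AR 0.5 | 10% | 0.96 | 5.7% | 5.7% | 4.6% |
| AR 0.5 | 30% | 0.89 | 6.9% | 8.0% | 5.0% |
| Random intercept + AR 0.5 | 10% | 0.91 | 6.6% | 7.3% | 5.2% |
| Random intercept + AR 0.5 | 30% | 0.87 | 7.4% | 8.7% | 5.1% |
| AR 0.7 | 0% | 0.99 | 5.0% | 5.4% | 4.8% |
| AR 0.7 | 10% | 0.90 | 6.9% | 7.6% | 5.3% |
| AR 0.7 | 30% | 0.83 | 8.4% | 10.1% | 5.3% |

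AR 0.8 to 0.9 gives about 9% to 13% two-sided over 10% to 50% crossover. True compound symmetry gives 4.4% to 5.5% two-sided at any crossover share. Adding month 1 widens the range to 7% to 13% one-sided and 7% to 18% two-sided.

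**Step 3: the worst month-6 scorers cross.** With AR 0.7 to 0.9 and 20% to 35% crossover (2,000 replicates), one-sided rejection is 7.4% to 10.4% under compound symmetry, 4.4% to 6.4% with sandwich errors and 4.4% to 7.0% with unstructured covariance. The SE ratio is 0.76 to 0.84.

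**Step 4: consistency.** If the standard error is r times its true value, one-sided rejection is 1 − Φ(1.645r). For r = 0.95 this is 5.9%; for r = 0.75 it is 10.9%. Nominal 95% intervals would need to be 1/0.95 = 1.05 to 1/0.75 = 1.33 times as wide.

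**The case against.** Four points have force.

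First, no declared test is affected. B.9.2.2 gives these endpoints no significance level, and B.8.2 sets no success criteria for secondary endpoints. The formal tests (Farrington-Manning, difference in proportions, two-sample t-test on VAS) are all at 3 months, before crossover, and none uses compound symmetry. This stands, and it limits the harm to intervals and nominal p-values.

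Second, the size cannot be derived from the documents. A reader might infer that the standard errors are simply wrong and that a 5% test rejects 9% to 10% of the time. The plan gives neither a correlation nor a crossover share. Change from baseline also puts the same baseline value into every visit, which adds an exchangeable component and makes pure autoregression the less favorable case. With a random intercept plus autoregression, inflation is more often 6% to 8% one-sided. This too stands.

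Third, a reader might also infer that visit-by-visit contrasts borrow one pooled variance. B.7.4 only summarizes the individual time points, and the month-3 VAS comparison in B.9.2.2 is a t-test on month-3 data, so that inference has no basis.

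Fourth, the analyses that censor data after crossover remove the switching. They are supplementary, however, and do not correct the current-treatment intervals.

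The plan's silence on robust errors does not prove that none would be used. The text as written simply does not require them.

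**Conclusion.** The point holds conditionally. Followed as written, the linear repeated-measures models understate the standard error of the treatment effect when correlation decays with time and a material share of subjects switch. With four visits and 10% to 35% crossover, that standard error is about 0.75 to 0.95 of its true value, and one-sided rejection at a nominal 5% is about 6% to 11%. It is about 5% if compound symmetry holds or nobody crosses.

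These figures assume 100 subjects followed to month 12, equal variances and no treatment effect. The mean estimate stayed near zero in the simulations, so the point concerns precision only; whether selective crossover biases the comparison is a separate question. Partly censored data were not simulated. The GEE models are protected if sandwich errors are used, which the plan does not state. The case for acting is that a better method is available at almost no cost, not that study success is in doubt.

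**What to change.** In B.9.2, specify for the linear repeated-measures models an unstructured covariance with small-sample degrees of freedom. If that model does not converge, or too few subjects remain at months 9 and 12, keep compound symmetry with subject-level sandwich standard errors. The fallback matters because the 100 subjects in B.5.5 are those who complete the primary assessment. Under B.7.2 that includes trial failures assessed at the end of the Trial Phase, and B.6.7 has them leave the study soon afterwards. State sandwich errors for the GEE models.

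Reconcile B.7.4, which describes tests of superiority and non-inferiority, with B.9.2.2, which assigns no hypothesis or significance level.

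The cost is SAP wording and a few degrees of freedom, with no change to sample size, conduct or data collection. Neither remedy is exactly nominal: sandwich errors reached 8.0% two-sided in the least favorable case tried (AR 0.9, 10% crossover, five visits). The unstructured model can also gain precision: at AR 0.9 with 20% crossover, the empirical SD of the estimate was 0.226, against 0.262 under compound symmetry.

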Written informed consent for participation in the study must be obtained from subjects before initiation of any study-related activities. Following informed consent, subjects will be assigned a unique subject identification number and will be considered to be enrolled in the study. Eligibility for advancing to the next stage of the study will be evaluated by the Investigator based on the defined inclusion and exclusion criteria. Subjects will be assessed for pain intensity and disability.

B.6.3. Entry Criteria Evaluation

The eligibility of subjects who have consented participation will be assessed based on the inclusion and exclusion criteria. Study subjects must meet all of the study inclusion criteria and none of the study exclusion criteria to be eligible. Assessments for eligibility include average pain intensity (which will be used as Baseline pain intensity), medication usage, medical records and history, and the Investigator's clinical judgment. Subjects with confirmed eligibility will proceed to Baseline assessment, while subjects who do not will be discontinued from the study.

B.6.4. Baseline

Before a subject is randomized, a subject will be requested to fill out standard questionnaires that will assess extent of disability, use of medications, and quality of life. The medical and surgical history of the subject will be collected. At this visit and subsequent visits, the subject will be assessed for adverse events, medication usage and be reminded to not increase pain medications from baseline through the 3-Month Visit.

Pre-operative assessments will follow the standard of care for SCS therapy and be determined by the site Investigator.

B.6.5. Randomization

Subsequent to completing Baseline assessments, qualifying subjects will be randomly assigned to either one of the two study treatment groups: DTM-SCS programming or Conventional SCS programming (active comparator). Randomization will be stratified by gender and whether the subject has leg pain or no leg pain at Baseline. Randomization will be done at each study site by randomly permuted blocks.

B.6.6. SCS Trial Phase

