A 10% margin has been previously used in a similar study.¹⁶ Meeting the statistical threshold for this test based on a 10% margin should produce clinically acceptable results.

B.9.2.2 Secondary Analyses

The following *secondary endpoints* will be evaluated:

- If the primary efficacy endpoint in the test group is found to be non-inferior to that in the control group, then a secondary endpoint will evaluate whether the proportion of subjects who achieve a 50% improvement in their back pain VAS score at 3 months in the test group is superior to that in the control group. A superiority test based on the difference in proportions will be performed based on the following null hypothesis, with a one-sided p-value of 0.05 or less considered evidence of statistical significance.

H_0 : The proportion of subjects (P) who achieve a 50% improvement in their back pain VAS score at 3 months in the Test group is less than or equal to that in the Control group.

$$P_{\text{Test}} \leq P_{\text{Control}}$$

H_1 : The proportion of subjects (P) who achieve a 50% improvement in their back pain VAS score at 3 months in the Test group is greater than that in the Control group.

$$P_{\text{Test}} > P_{\text{Control}}$$

- Change in mean VAS will be evaluated with two-sample t-test of non-inferiority in means with a 0.65 cm margin at 3 months.

H_0 : The change (C) in subject's VAS pain intensity score relative to baseline at the Primary Efficacy Assessment in the Test group is inferior to that of subjects in the Control group (active control).

$$C_{\text{Test}} \geq C_{\text{Control}} - 0.65 \text{ cm}$$

H_1 : The change (C) in subject's VAS pain intensity score relative to baseline at the Primary Efficacy Assessment in the Test group is not inferior to that of subjects in the Control group (active control).

$$C_{\text{Test}} < C_{\text{Control}} - 0.65 \text{ cm}$$

The non-inferiority margin of 0.65 cm was selected based on a previous study of a similar therapy against traditional SCS¹⁶. In that study, the experimental therapy showed a 4.9 point improvement while traditional SCS showed a 3.6 point improvement for a difference of 1.3 points. Taking 50% of this treatment effect yields the margin of 0.65.

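### The named 3-month tests adjust for neither the randomization strata nor baseline VAS: valid as planned, with a small optional gain for two secondary tests

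*Combined protocol and SAP*

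**What the plan says.** **Design.** B.6.5 says "Randomization will be stratified by gender and whether the subject has leg pain or no leg pain at Baseline" and also "Randomization will be done at each study site by randomly permuted blocks". B.6.3 takes the entry pain score as the baseline, so baseline VAS is fixed before allocation.

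**Tests at 3 months.** Three are named:

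- Primary (B.9.2.1): the responder endpoint "will be evaluated with a Farrington-Manning binomial test for non-inferiority with a 10% margin at the one-sided 0.05 alpha level".
- Responder superiority (B.9.2.2), once non-inferiority is shown: "A superiority test based on the difference in proportions will be performed", at one-sided 0.05.
- VAS change (B.9.2.2): a two-sample t-test with a 0.65 cm margin.

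None of them names a stratum or covariate. Baseline VAS enters only as a reference value: for response (B.7.3), "A decrease in back pain VAS by at least 50% at 3 months after Permanent Device Activation as compared with Baseline", and for the change score (B.7.4).

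**Related text.** The repeated-measures wording in B.7.4, B.9.2 and B.9.2.2 gives a covariance structure and a time-dependent treatment status, but no strata and no baseline covariate. B.9.2.4 refers to a separate statistical analysis plan for imputation details only. That plan is not among the documents.

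**The concern.** Factors used to stratify randomization are usually carried into the analysis. If they predict outcome, balancing on them and then ignoring them makes the test somewhat conservative and gives up precision. A raw change score is also inefficient when baseline and follow-up are weakly correlated. That is plausible here, because entry requires a back pain VAS of at least 6.0 cm and so narrows the baseline range.

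What is at stake is precision in two secondary tests. B.8.2 rests study success on the primary non-inferiority test and says "There are no additional pre-specified subject or study-level success criteria for secondary and tertiary endpoints". The superiority test nevertheless has its own significance rule and modest power, so a gain that needs no added patients deserves a look.

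**Working it through.** **1. The plan's own figure.** Inputs from B.5.5.1: 70% against 50%, margin 10 points, one-sided 0.05, 50 per arm, power about 90% or greater. The rates fitted under the null (difference -0.10) are 0.544 and 0.644, so the null variance sum is 0.4773. Under the alternative it is 0.7×0.3 + 0.5×0.5 = 0.46.

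Power = Φ[(0.30 − 1.645×√(0.4773/50)) / √(0.46/50)] = Φ[(0.30 − 0.1607)/0.0959] = Φ(1.45) = 0.927. Exact enumeration also gives 0.927, so the stated power is met.

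**2. Superiority at the same rates.** The pooled rate is 0.6, so the null variance sum is 0.48.

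Power = Φ[(0.20 − 1.645×√(0.48/50)) / 0.0959] = Φ(0.405) = 0.657; exact 0.658. With 25% attrition the plan randomizes 100/0.75, about 134 subjects. If all were analysed (67 per arm), exact power would be 76.5% for superiority and 97.5% for the primary test.

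**3. Validity of the planned tests.** The exact one-sided size of the unadjusted primary test at 40% against 50% is 0.047. Over control rates of 20–90% it is at most 0.055, and that excess comes from discreteness, not from missing adjustment. In simulations with stratified blocks, unadjusted size was 0.038–0.053 (non-inferiority) and 0.033–0.048 (superiority), lowest where the strata were strongly prognostic.

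**4. Gain for the responder tests.** Assumed, because the documents do not give them: blocks of 4, gender 50/50, and response gaps of 0, 10 or 20 points for each factor. Entries are power changes in points, stratified minus planned, from 60,000 simulated trials per setting, with 20 sites (the plan's maximum).

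| Setting | Primary (gap 0/10/20) | Superiority (gap 0/10/20) |
|---|---|---|
| 100 subjects, leg pain 50%, blocks by site and stratum | -0.5 / -0.1 / +1.0 | -0.6 / 0.0 / +2.5 |
| Same, leg pain 80% | -0.4 / -0.2 / +0.8 | -0.8 / -0.2 / +1.8 |
| Same, leg pain 90% | -0.5 / -0.3 / +0.4 | -0.8 / -0.3 / +1.4 |
| 100 subjects, leg pain 80%, blocks by stratum only | -0.2 / +0.2 / +0.8 | -0.1 / +0.5 / +2.5 |
| 134 subjects, leg pain 80%, blocks by site and stratum | -0.2 / -0.2 / +0.3 | -0.7 / -0.2 / +1.7 |

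The 100-subject rows start from about 93% and 66%, the 134-subject row from about 97.5% and 76.5%. A 30-point gap per factor is left out as extreme: at a 50% leg-pain share one test-arm stratum would respond at 70 + 15 + 15 = 100%.

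A gender by leg-pain cell with no subject in one arm arose in 0%, 2% and 27% of simulated trials at leg-pain shares of 50%, 80% and 90%. Adding site would give up to 20×4 = 80 cells for about 135 subjects, or 1.7 per cell, so site is not a workable stratum.

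**5. Gain for VAS change.** Let s0 and s1 be the baseline and follow-up SDs and r their correlation. Change-score variance is s0² + s1² − 2·r·s0·s1, and ANCOVA residual variance is s1²(1 − r²). The proportional reduction is (s0 − r·s1)² divided by the change-score variance. Three covariates with 100 subjects cost a factor of about 97/94 = 1.032.

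The documents give no SD or correlation. A baseline uniform on 6–10 cm has SD 4/√12 = 1.15; the other inputs are assumed.

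| s1, s0, r | Change score | ANCOVA | Ratio | Ratio × 1.032 |
|---|---|---|---|---|
| 2.0, 1.15, 0 | 5.32 | 4.00 | 0.75 | 0.78 |
| 2.5, 1.15, 0.1 | 7.00 | 6.19 | 0.88 | 0.91 |
| 2.5, 1.0, 0.4 | 5.25 | 5.25 | 1.00 | 1.03 |

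Simulation at 50 per arm, with gender and leg pain non-prognostic, agrees. The variance ratio was 0.778–1.032 over s1 = 2.0–3.0 and r = 0–0.5, and 0.908–1.031 at s1 = 2.5 and r = 0.1–0.5. At s1 = 2.5 a gain needs a correlation below about 0.3. In that narrower range, a non-inferiority test with a 0.65 cm margin (one-sided 0.05 assumed) changes in power by -1.0 to +2.1 points at no true difference (from 33–44%), and by -0.9 to +2.9 points at a true 0.65 cm advantage (from 79–91%).

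**The case against.** The strongest reply is that an unadjusted valid test is a legitimate choice which no section contradicts, and that the responder figures hardly argue for changing it. At gaps of 0 or 10 points the superiority change is zero or negative in 9 of the 10 entries above, the best being +0.5. A consistent gain needs a 20-point gap on both factors, and no section says that either factor predicts response. The VAS gain depends on a low correlation that the documents do not give. All of this stands, and it is why the point is optional and the primary test is left alone.

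Three further limits also stand:

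- B.7.4 assigns both secondary endpoints to repeated-measures models, while B.9.2.2 names single-time tests at 3 months. Any adjustment has to follow whichever analysis is kept.
- The VAS hypotheses need attention first. B.7.4 says "A negative result reflects a decrease in the Pain VAS, while a positive result reflects an increase in Pain VAS", so the alternative printed in B.9.2.2 (test change below control change minus 0.65 cm) demands superiority by 0.65 cm under a non-inferiority label. That is a separate issue and matters more than the covariates.
- B.9.2.4 keeps other analyses on evaluable data unless otherwise specified, and leaves imputation details to the separate plan. No rule for pooling a stratified test over imputations is therefore proposed here.

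What the objection does not remove is that the trial already collects these factors and that using them costs little.

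**Conclusion.** The omission is real and the consequence is small. For VAS change, ANCOVA variance would lie between about 22% below and 3% above the t-test's, with the gain at low correlation. For responder superiority, the change is about -1 to +2.5 power points. These ranges rest on assumed SDs, correlations, block size, leg-pain share and response gaps.

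A reader might infer more than this, in three ways:

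- That ignoring the strata invalidates the tests or inflates type I error. The size calculations show nominal or slightly conservative behaviour.
- That the trial is underpowered for its primary aim or that study success is at risk. Power is 92.7% against a target of about 90%, and no success criterion depends on the secondary tests.
- That stratifying shows the factors to be prognostic, so that a gain is assured. No section gives a reason for choosing them, and without prognostic strength the change is nil or slightly negative.

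If the separate statistical analysis plan already adjusts, nothing remains of the point.

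**What to change.** Before outcome data are seen, add a few lines to B.9.2.2 or to the separate statistical analysis plan:

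- **VAS change.** Once the hypotheses and the non-inferiority label are reconciled, replace the two-sample t-test with ANCOVA of 3-month change on treatment, baseline VAS, gender and leg pain.
- **Responder superiority.** Pre-specify a stratified score test with Mantel-Haenszel weights over the four gender by leg-pain cells as randomized, without site, at the same one-sided 0.05. If a cell has no subject in one arm, merge the two gender cells within that leg-pain level.
- **Primary test.** Leave Farrington-Manning, its margin and its alpha unchanged.
- **Sensitivity.** Keep the unadjusted superiority test and t-test as sensitivity analyses.
- **Consistency.** State whether the repeated-measures or the single-time analysis is kept for each secondary endpoint, and use the same factors in it.

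The change needs no new data and no added patients. If the factors are not prognostic, it costs under about 1 point of superiority power and up to about 3% more VAS variance (about 1 point of VAS power).
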